For subjects who newly flare at any time during the 1st 52 weeks of Part B and require a treatment change, open-label sirukumab 100 mg SC q2w can be initiated within the first 52 weeks of Part B. The duration of treatment will be at the discretion of the investigator but must not exceed 52 weeks. Treatment with open-label sirukumab 100 mg SC q2w must complete by Week 104 (the end of the extension phase). Corticosteroid use or the initiation of methotrexate therapy alone or in addition to sirukumab treatment during Part B will be at the discretion of the investigator.

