**Part B: 104-week long-term extension phase**

Objectives	Endpoints

 
To evaluate the long-term maintenance of disease remission on cessation of 12 months of sirukumab treatment
 
	
 
Proportion of subjects who remained in sustained remission without requirement for rescue therapy or treatment change at Week 24 of Part B
 
Proportion of subjects in sustained remission over time
 
Time to first GCA flare for subjects in sustained remission at baseline of Part B
 
Number of disease flares per patient over time
 
Proportion of subjects requiring hospitalizations for disease flare and number of hospitalizations for disease flare over time
 
Proportion of subjects who remained in sustained remission without requirement for rescue therapy or treatment change 6 months post cessation of 12-month sirukumab treatment
 

 
To assess the effect of sirukumab treatment on health-related quality of life, GCA and/or steroid-related symptoms and disability by patient and clinician reported outcomes over time
 
	
 
Patient reported outcomes including SF-36v2, EQ-5D (5L), FACIT-Fatigue, Pain NRS, Steroid Impact PRO, HAQ-DI and PtGA
 
Clinician reported outcomes including PhGA
 

 
To assess long-term cumulative prednisone doses
 
	
 
Median and cumulative prednisone dose over time
 

 
To assess the long-term safety of sirukumab
 
	
 
Incidence of adverse events and serious adverse events, changes in vital signs, hematology and clinical chemistry parameters
 

 
To investigate long-term corticosteroid-related toxicities
 
	
 
Incidence of corticosteroid-related adverse events
 

 
To evaluate immunogenicity of subcutaneously administered sirukumab in subjects receiving open-label sirukumab
 
	
 
Serum anti-sirukumab antibodies
 

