Arm C	Sirukumab 50 mg SC q4w for 52-weeks plus a prespecified maximum of 6-month prednisone taper regimen	Sirukumab 50mg SC q4w + 6 month prednisone
Arm D	Placebo SC q2w for 52 weeks plus a prespecified maximum of 6-month prednisone taper regimen	Placebo SC q2w + 6 month prednisone
Arm E	Placebo SC q2w for 52 weeks plus a prespecified maximum of 12-month prednisone taper regimen	Placebo SC q2w + 12 month prednisone

It is important to note that prednisone intake will be recorded from different sources:

- Prednisone taken prior to screening: recorded on the “Prior Concomitant Medications - (Screening)” eCRF page

- Prednisone taken as part of the pre-specified taper (prednisone study drug):
 - Open-label portion – recorded in “Prednisone - Open Label” eCRF page
 - Blinded portion – recorded in “Prednisone - Blinded Taper” eCRF page
- Concomitant Prednisone – recorded on the “Concomitant Medications – Corticosteroids” eCRF page.

For more details, please refer to [Section 7](#).

Two types of rescue medication can be identified:

- Those from the “Concomitant Medications – Non Corticosteroids” eCRF page when the questions regarding Rescue Medication is ticked as "Yes" and the drug identified as GCA-related
- Those from the “Concomitant Medications – Corticosteroids” eCRF page when the question regarding Rescue Medication is ticked as "Yes" and the unit is not:
 - Actuation
 - Application
 - Area under curve
 - Cubic centimeter
 - Cells
 - Cells per kilogram
 - Fingertip unit
 - Drops
 - Gum
 - Inhalation
 - Kilocalories
 - Minimum alveolar concentration
 - Mega becquerels (MBq)
 - Millicurie
 - Nebule
 - Patch
 - Powder
 - Puff
 - Ring
 - Spray
 - Suppository

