7.1. Prior and Concomitant Medications

Prior and concomitant medications are recorded on 3 different concomitant medications eCRF pages:

- Prior Concomitant Medications form
- Concomitant Medications – Non-Corticosteroids
- Concomitant Medications – Corticosteroids

Prior and concomitant medications will be coded using GSK Drug coding dictionary, summarized separately on the Safety set and each summary will be split by corticosteroids and non-corticosteroids. All prior and concomitant medications will be listed for the Safety set.

In this study, prior medications are defined as those medications with a recorded start date prior to the initiation of SC IP. Prior medications are collected at Screening and are noted as to whether they are cardiovascular, GCA related, non-GCA related or corticosteroid medications.

Concomitant medications for Part A are defined as those medications which are taken on or after the initiation of SC IP in Part A, up to the Week 52 visit or the first SC IP of Part B open-label treatment, whichever is earlier for subjects participating in Part B.

Concomitant medications taken during the 16-weeks Safety follow-up visit will be summarized in Part A or Part B as relevant.

Concomitant medications where the eCRF option “Was drug administered as a rescue medication” is selected as “Yes” and that are corticosteroids when the unit is not in (Actuation, Application, Area under curve, Cubic centimeter, Cells, Cells per kilogram, Fingertip unit, Drops, Gum, Inhalation, Kilocalories, Minimum alveolar concentration, Mega becquerels (MBq), Millicurie, Nebule, Patch, Powder, Puff, Ring, Spray, suppository) or non-corticosteroid and GCA related will be considered as rescue therapies.

Three summary tables will be displayed:

- Prior medications
- Concomitant medications – rescue therapies
- Concomitant medications – non-rescue therapies

A listing of all rescue medications will be produced.

Each of the 3 summary table will be split by medication type: corticosteroids or non-corticosteroids. Within each byline, medications will be presented in the descending order of total incidence (i.e., summed across all treatment groups) by Anatomical Therapeutic Chemical (ATC) level 1 and ingredient for the Safety set.

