11.4. Efficacy Analysis

11.4.1. Endpoints Specific to Part B

The following endpoints are specific to Part B and will be displayed only on the subset of subjects in sustained remission at the Week 52 visit of Part A and enrolled in Part B:

- Proportion of subjects in sustained remission over time (including week 24):
Subjects who remained in sustained remission without requirement for rescue therapy or treatment change at each scheduled visit of Part B will be defined as subjects having achieved all of the following criteria:
Subjects in sustained remission at the Week 52 visit of Part A, as defined in [Section 8.1](#).

AND

Absence of disease flare:

Flare is determined by the investigator and defined as the recurrence of symptoms attributable to active GCA, with or without elevations in ESR and/or CRP.

The following rule will be used to assess absence of disease flare:

“Has the patient flared since their last visit?” should be answered “No” at each scheduled and unscheduled visit from any Part B visit up to Week X visit of Part B on the Clinical Assessment of GCA eCRF page.

AND

No requirement for rescue therapy at any time through Week X of Part B

If any concomitant corticosteroid medication when the unit is not in (Actuation, Application, Area under curve, Cubic centimeter, Cells, Cells per kilogram, Fingertip unit, Drops, Gum, Inhalation, Kilocalories, Minimum alveolar concentration, Mega becquerels (MBq), Millicurie, Nebule, Patch, Powder, Puff, Ring, Spray, Suppository) or any of concomitant non-corticosteroid medication identified as “GCA related” with the question “Was drug administered as a rescue medication?” ticked as “Yes” and if the first SC IP date \leq Concomitant medication start date \leq Week X visit date, then the subject will fail the criterion.

AND

No requirement for treatment change at any time through Week X of Part B

If any OL Sirukumab dose is taken prior or on the Week X visit of Part B, subject will fail the criterion.

If all of the 4 criteria are met, subject will achieve the endpoint at the Week 24 visit of Part B. If 1 of the 4 criteria is not met, the subject will be considered as not meeting the endpoint. For more details on imputation of missing data for the primary endpoint, please refer to [Section 4.6.2.1](#).

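### In SAP 11.4.1, Part B prednisone or methotrexate given for GCA with no rescue tick and no recorded flare counts as neither rescue nor treatment change

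*SAP*

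**What the plan says.** Protocol Section 3 defines the endpoint for Part B's first objective as "Proportion of subjects who remained in sustained remission without requirement for rescue therapy or treatment change at Week 24 of Part B". Rescue therapy and treatment change are named separately.

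SAP 11.4.1 turns this into four criteria, and all must hold: sustained remission at Week 52 of Part A, no recorded flare, "No requirement for rescue therapy at any time through Week X of Part B", and "No requirement for treatment change at any time through Week X of Part B". They combine strictly: "If 1 of the 4 criteria is not met, the subject will be considered as not meeting the endpoint". The only rule under the treatment-change heading is "If any OL Sirukumab dose is taken prior or on the Week X visit of Part B, subject will fail the criterion".

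The rescue criterion relies on an eCRF tick. SAP 3.3 takes a corticosteroid as rescue "when the question regarding Rescue Medication is ticked as" Yes, subject to a list of excluded units. SAP 7.1 opens its definition with the same tick and applies it to corticosteroids "or non-corticosteroid and GCA related will be considered as rescue therapies".

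Protocol Section 1 (Treatment Arms and Duration) and Section 4.2.2 leave the following to the investigator: "Corticosteroid use or the initiation of methotrexate therapy alone or in addition to sirukumab treatment during Part B".

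**The concern.** The endpoint is meant to show how well remission holds once sirukumab has stopped. A subject who has begun new GCA treatment is not showing that, whatever box was ticked on the form.

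The rescue and flare criteria catch many such subjects, but not all. Flare is defined by recurrence of symptoms. Under Protocol 6.4 the masking of ESR and CRP ends with Part A, and Protocol Tables 3 to 5 schedule both markers through Part B. An investigator who starts prednisone or methotrexate because a marker is rising, in a subject without symptoms, can properly answer No to the flare question. Whether the drug is then ticked as rescue is a matter of judgement. The protocol describes its rescue regimen for the 52-week double-blind period (Sections 4.2.1, 5.4.1 and 6.3) and does not define rescue for Part B. If the tick is absent, only the treatment-change criterion could catch the subject, and it looks only at open-label sirukumab.

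**Working it through.** The point concerns a derivation rule, and the plan has no figure to reproduce. The check applies the four criteria of SAP 11.4.1 to every way the eCRF could record one situation: a subject in sustained remission at Part A Week 52 who takes no open-label sirukumab and starts prednisone (in mg) or methotrexate in Part B.

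**Inputs.** Flare recorded, Yes or No. Rescue tick, Yes or No. For methotrexate, marked GCA related, Yes or No. Patterns: prednisone 2 × 2 = 4; methotrexate 2 × 2 × 2 = 8; total 12.

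**Two readings of the rescue sentence in 11.4.1.** Reading 1 applies the rescue tick to both drug types, as SAP 3.3 and 7.1 do. Reading 2 takes the tick to qualify only the non-corticosteroids, which the word order in 11.4.1 also allows.

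| Drug | Flare | Rescue tick | GCA related | Patterns | Reading 1 | Reading 2 |
|---|---|---|---|---|---|---|
| Prednisone | No | No | n/a | 1 | counts | fails |
| Prednisone | No | Yes | n/a | 1 | fails | fails |
| Prednisone | Yes | either | n/a | 2 | fails | fails |
| Methotrexate | No | No | No | 1 | counts | counts |
| Methotrexate | No | No | Yes | 1 | counts | counts |
| Methotrexate | No | Yes | No | 1 | counts | counts |
| Methotrexate | No | Yes | Yes | 1 | fails | fails |
| Methotrexate | Yes | either | either | 4 | fails | fails |

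Still counted as in sustained remission: Reading 1, 1 + 3 = 4 of 12; Reading 2, 0 + 3 = 3 of 12. These are logical patterns, not subjects.

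The patterns that count are not equally wrong. Methotrexate marked GCA related, with no tick and no flare, is a clear misclassification under both readings. Unticked prednisone for GCA with no flare is one under Reading 1. Methotrexate not marked GCA related may have been given for another reason or may be a recording error.

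**Direction and size.** If *m* of the *n* subjects analysed in an arm fall in this gap, the reported proportion is too high by 100 × *m*/*n* percentage points. It cannot be too low for this reason. The documents give neither *m* nor *n*.

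**Whether another output covers the gap.** SAP 7.3 names two categories of concomitant corticosteroid: ticked as rescue, and ticked as not GCA related. GCA-directed prednisone with neither tick is in neither category. SAP 11.4.2 counts only rescue corticosteroids in Part B cumulative prednisone, so the same course is missing there as well.

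**The case against.** The strongest reply is that the SAP divides the work sensibly: open-label sirukumab is the treatment change, and corticosteroid or methotrexate is rescue. Protocol 4.2.2 does use the term treatment change when it describes starting open-label sirukumab after a new flare. It deals with corticosteroid and methotrexate in a separate sentence and does not call them treatment changes. Protocol 5.4.1 treats both as a rescue regimen in the double-blind period. A reader might infer that the protocol lists three kinds of Part B treatment change. It does not; the term is left undefined. Its use is not confined to sirukumab either: Protocol 6.4 speaks of an ESR alert helping to decide on a treatment change in Part A, where open-label sirukumab is unavailable. The SAP's division is defensible, but it works only if every GCA-directed start is ticked as rescue, and nothing in the documents requires that in Part B.

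A reader might also infer that anyone given prednisone or methotrexate in Part B still counts as in remission. That goes too far. Under Reading 1, 8 of the 12 patterns fail; under Reading 2, every prednisone pattern fails.

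Finally, the consequence is limited, and this stands. SAP 1.1 and Section 8 reduce efficacy to summary statistics after termination. The opening of SAP Section 11 restricts Part B displays to demographics, baseline characteristics and safety, which conflicts with 11.4. Listings of concomitant medication, corticosteroid details and each criterion would let a careful reader find the affected subjects, although the headline proportion would not change.

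**Conclusion.** The gap is real but narrow. GCA-directed prednisone or methotrexate in Part B, with no rescue tick and no recorded flare, passes all four criteria, and the subject is reported as in remission with neither rescue nor treatment change. For methotrexate this holds under either reading of the rescue sentence; for prednisone it depends on the tick applying to corticosteroids, as SAP 3.3 and 7.1 indicate. The effect can only be upward.

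Two stronger conclusions are tempting and unsupported. One is that the error favours the sirukumab arms because CRP rises as the drug washes out and prompts treatment. The documents support the end of marker masking, but they give no rate of such rises, of treatment without symptoms, or of unticked use, by arm or overall. The other is a size in percentage points. At the planned 70% rate, Arm A would have 0.70 × 51 = 35.7, about 36 responders, so each misclassified subject would add 1/36 = 2.8 points. That denominator belongs to the full planned enrolment. SAP 1.1 says few subjects reached Week 52, and SAP 4.1 sets the sample at the number randomized by termination. How many subjects fall in the gap is unknown, so no total can be given.

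This is a cheap correction worth making if the Part B proportion is reported.

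**What to change.** In SAP 11.4.1, derive treatment change as any of the following after the Part A Week 52 visit and up to the Week X visit:

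- any open-label sirukumab dose;
- any start or dose increase of a systemic corticosteroid not ticked as non-GCA related;
- any start or dose increase of methotrexate or another GCA-related immunosuppressant.

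Apply this whatever the rescue tick or flare answer, and list which item caused each failure. Under this rule all 12 patterns above fail, provided the prednisone is not ticked as non-GCA related.

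Reword the rescue sentence so it is clear whether the tick applies to corticosteroids as well as non-corticosteroids. Reconcile the opening of Section 11 with 11.4 on whether the endpoint is displayed.

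The cost is SAP wording and a little programming from concomitant-medication pages already collected. Reported Part B remission rates may fall slightly. Clinical management does not change.

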## 7. STUDY ASSESSMENTS AND PROCEDURES

Protocol waivers or exemptions are not allowed with the exception of immediate safety concerns. Therefore, adherence to the study design requirements, including those specified in the Time and Events Tables, are essential and required for study conduct.

This section lists the procedures and parameters of each planned study assessment. It should be noted that for those subjects with disease flare at any visit, the assessments to

be performed are those specified in the Early Withdrawal or Flare visit in all of the following Time and Events Tables.

The assessments for Part A of the study are provided in Time and Events [Table 2](#) in Section [7.1](#).

Part B assessments are included in separate Time and Events Tables ([Table 3](#), [Table 4](#) and [Table 5](#)). It should be noted that the Week 52 visit of Part A also serves as the Week 0 visit of Part B of the study.

Part B Time and Events Tables should be followed as described below:

Time and Events [Table 3](#): Assessments for subjects who will **not** receive open-label treatment with sirukumab during Part B. Dispensing of investigational product is not required. Hematology and clinical chemistry assessments and pregnancy testing from the Week 16 visit onwards are also not required as subjects will have completed the 16-week post-drug follow up assessments.

Time and Events [Table 4](#): Assessments for subjects who initiate open-label sirukumab treatment **at** the baseline visit of Part B (those with disease activity or flare at the Week 52 visit of Part A).

Time and Events [Table 5](#): Assessments for subjects who initiate open-label sirukumab treatment **after** the baseline visit and anytime up to the Week 52 visit of Part B (those who flare during Part B). These subjects will initially be following the assessments in Time and Events [Table 3](#) and will undergo the assessments scheduled for that visit and will include initiation of open-label sirukumab treatment at that same visit.

Subsequent visits will follow the assessments from Time and Events [Table 5](#) starting from the visit labelled 'plus 2 weeks' onwards. It is important that upon initiation of open-label sirukumab therapy, the next visit should occur **2** weeks after treatment start. For these subjects, the last visit in Part B should be scheduled for when they have been in Part B for 104 weeks or upon completion of the 16-week follow-up if applicable.

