12. On study drug administration days, Pharm serum samples must be collected prior to study drug administration. Blood collected from one venipuncture will be divided into multiple aliquots of serum for Pharm serum (sirukumab concentration and antibodies to sirukumab) and backup samples.
13. To be collected only for those subjects consenting to provide samples for the biobank for future exploration of GCA disease biology.
14. Sample should be collected at the baseline visit but may be collected at any visit post-baseline if not collected at the baseline visit.
15. Selected sites participating in the exploratory US imaging portion only; restricted to subjects with new onset disease
16. Optimally (but not required), to be performed prior to or within 3 days of the start of prednisone.

**Table 3 Time and Events Table for Part B of the Study (104-week Extension): Subjects NOT Receiving Open-label Sirukumab During Part B**

	Wk 0/(Wk 52 of Part A)	wk 4±5d	wk 8±5d	wk 12±5d	wk 16±5d	wk 24±5d	wk 36±5d	wk 52±5d	wk 76±5d	wk 104±5d	Flare	Early Withdrawal
Concomitant Medications	x	x	x	x	x	x	x	x	x	x	x	x
Assess Invest. Product compliance 	x											
Efficacy Assessments												
GCA disease activity	x	x	x	x	x	x	x	x	x	x	x	x
PGA (patient, physician) 	x	x	x	x	x	x	x	x	x	x	x	x
Health Outcomes												
Pain NRS 	x	x	x	x		x		x	x	x	x	x
HAQ-DI 	x			x		x		x	x	x	x	x
FACIT-Fatigue 	x			x		x		x	x	x	x	x
Steroid Impact 	x			x		x		x	x	x	x	x
SF-36v2 (acute) 	x			x		x		x	x	x	x	x
EQ-5D (5L) 	x			x		x		x	x	x	x	x
Safety Assessments												
Physical Examination 	x							x		x	x	x
Vital Signs 	x	x	x	x	x	x	x	x	x	x	x	x
TB evaluation 	x	x	x	x	x							x 
Height and weight	x									x	x	x
Adverse Events	x	x	x	x	x	x	x	x	x	x	x	x
C-SSRS 	x	x	x	x	x						x	x
Laboratory Assessments												
Hematology	x	x	x	x	x						x 	x 
Serum chemistry	x	x	x	x	x						x 	x 
CRP	x	x	x	x	x	x	x	x	x	x	x	x

	Wk 0/(Wk 52 of Part A)	wk 4±5d	wk 8±5d	wk 12±5d	wk 16±5d	wk 24±5d	wk 36±5d	wk 52±5d	wk 76±5d	wk 104±5d	Flare	Early Withdrawal
ESR	x	x	x	x	x	x	x	x	x	x	x	x
Lipid panel (fasting)	x			x	x						x 	x 
Hemoglobin A1c	x			x	x						x 	x 
Pregnancy Test 	U	U	U	U	U							U 

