6. Pregnancy test: urine = U, serum = S. Premenopausal women only. A urine pregnancy test should be performed every 4 weeks while taking open-label sirukumab and for 16 weeks post discontinuation of sirukumab treatment. Subjects should perform a urine pregnancy test at home when there is no study visit corresponding to the 4-weekly interval. Pregnancy test kits will be provided by the central laboratory for subject use at home.
7. On study drug administration days, Pharm serum samples must be collected prior to study drug administration. Blood collected from one venipuncture will be divided into multiple aliquots of serum for Pharm serum (sirukumab concentration and antibodies to sirukumab) and backup samples..
8. For subjects participating in the exploratory US imaging cohort. Ultrasound scans to be performed only in the event of disease flare or relapse in Part B. Part B scans will conclude when the last subject in the US imaging cohort completes Part A.

**Table 5 Time and Events Table for Part B (104-week Extension) of the Study: Subjects Receiving Open-label Sirukumab at Any Time AFTER (but NOT immediately Upon) Entry into Part B**

	Start of open-label sirukumab 	PLUS 2 Wks±5d	PLUS 4 Wks±5d	PLUS 8 Wks±5d	PLUS 12 Wks±5d	PLUS 16 Wks±5d	PLUS 24 Wks±5d	PLUS 36 Wks±5d	PLUS 48 Wks±5d 	PLUS 52 Wks±5d	PLUS 76 Wks±5d	PLUS 104 Wks±5d 	Flare	Early Withdrawal	Follow Up
Dispense Investigational Product		X	X	X	X	X	X	X	X						
Assess Invest. Product compliance		X	X	X	X	X	X	X		X	X	X	X	X	
Concomitant Medications		X	X	X	X	X	X	X		X	X	X	X	X	X
Efficacy Assessments															
GCA disease activity	X	X	X	X	X	X	X	X		X	X	X	X	X	
PGA (patient, physician) 		X	X	X	X	X	X	X		X	X	X	X	X	
Health Outcomes															
Pain NRS 		X	X	X	X		X			X	X	X	X	X	
HAQ-DI 					X		X			X	X	X	X	X	
FACIT-Fatigue 					X		X			X	X	X	X	X	
Steroid Impact 					X		X			X	X	X	X	X	
SF-36v2 (acute) 					X		X			X	X	X	X	X	
EQ-5D (5L) 					X		X			X	X	X	X	X	
Safety Assessments															
Physical Examination 										X		X	X	X	X
Vital Signs 		X	X	X	X	X	X	X		X	X	X	X	X	X
TB evaluation 		X	X	X	X	X	X	X		X	X	X		X	
Height and weight												X	X	X	
Adverse Events		X	X	X	X	X	X	X		X	X	X	X	X	X
C-SSRS 	X	X	X	X	X	X	X	X		X	X	X	X	X	X
Laboratory Assessments															
Hematology		X	X	X	X	X	X	X		X	X	X	X	X	

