Serum chemistry		X	X	X	X	X	X	X		X	X	X	X	X	

	Start of open-label sirukumab 	PLUS 2 Wks±5d	PLUS 4 Wks±5d	PLUS 8 Wks±5d	PLUS 12 Wks±5d	PLUS 16 Wks±5d	PLUS 24 Wks±5d	PLUS 36 Wks±5d	PLUS 48 Wks±5d 	PLUS 52 Wks±5d	PLUS 76 Wks±5d	PLUS 104 Wks±5d 	Flare	Early Withdrawal	Follow Up
CRP		x	x	x	x	x	x	x		x	x	x	x	x	
ESR		x	x	x	x	x	x	x		x	x	x	x	x	
Lipid panel (fasting)					x	x	x	x		x	x	x	x	x	
Hemoglobin A1c					x	x	x	x		x	x	x	x	x	
Pregnancy Test 			U	U	U	U	U	U	U	U	U	U		U	U
PK 					x					x		x	x	x	x
Immunogenicity 					x					x		x	x	x	x
Exploratory US Imaging															
Ultrasound imaging 													x		

1. Upon the initiation of open-label sirukumab, perform the assessments from Time and Events [Table 3](#) at the visit the subject was scheduled to undergo when study drug is started.
2. Visit only to dispense IP; no assessments are required.
3. Although this visit is labelled as 104 weeks since the start of open-label sirukumab, it does not take into account the exact start time, since this will be different for each subject depending upon when in the first 52 weeks of Part B open-label sirukumab was started. The important point to note, is that this last visit should be scheduled when each of these subjects will complete 104 weeks in Part B.
4. PROs to be completed by subjects before other clinically evaluated assessments or blood draws and before the administration of study drug. At visits where subject is fasting for blood draws, the option exists to perform blood draws prior to completing PROs as necessary to end the fast. HAQ-DI administered only to sub-set of subjects with PMR. PGA assessed using PtGA (subjects) and PhGA (physicians, after subject completion of questionnaires and after conducting patient assessments). .
5. Brief physical exam.
6. Measure in a semi-supine position after 5 minutes rest; includes blood pressure, temperature and heart rate.
7. Suggested questions (see Section [7.5.7](#)). A QuantiFERON-TB Gold Test should be performed at any time during the study if TB is suspected.

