Given study termination, only the subset of subjects who attended the Week X visit of Part B or who discontinued study treatment or withdrew from study prior to the 10th of October 2017 will be included in this analysis.

The proportion of subjects achieving the endpoint over time will be presented by Part A treatment group. Subjects achieving the endpoint will be categorized by the criterion they failed to achieve. A listing will be produced with the detail of each criteria met or not met over time.

- Time to first disease flare for subjects in sustained remission at Baseline of Part B:

Only subjects who achieve sustained remission at the Week 52 visit of Part A will be included in this analysis.

Time to first disease flare after clinical remission is the time (days) from the Week 52 visit date to the earliest disease flare date:

Subjects without disease flare at the time of the analysis will be censored at the date of their last visit.

A Kaplan-Meier analysis will be summarized. The number of subject achieving clinical remission, as well as the number of subjects with a disease flare and the number of subjects censored with their censoring reasons will be summarized. 25th percentile, median and 75th percentile time to first flare will be summarized in days for each treatment group.

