11.6. Visit-based outputs

All outputs displaying Part B visit will use a mapped visit in relation to the Baseline of Part B.

For example, if a subject starts OL Sirukumab at the Week 24 Visit of Part B, the visit 2 weeks after initiation of OL Sirukumab will be mapped Week 26 Visit of Part B.

All listings displaying data by visit will show both the original visit collected and the mapped visit. For example, a subject that flares and has a Week 12 PLUS 2 visit would have the following original and mapped visits:

- Original: Week 12 PLUS 2 Weeks Visit
- Mapped: Week 14 Visit

Note that the visit mapping will only affect subjects receiving OL Sirukumab at any time after (but not immediately upon) entry into Part B.

12. References

International Council for Harmonisation. ICH harmonised tripartite guideline: Statistical principles for clinical trials E9. 1998 [cited 2017 Feb 06]. Available from:
http://www.ich.org/fileadmin/Public_Web_Site/ICH_Products/Guidelines/Efficacy/E9/Step4/E9_Guideline.pdf

http://www.euroqol.org/fileadmin/user_upload/Documenten/PDF/Folders_Flyers/EQ-5D-5L_UserGuide_2015.pdf

Hsieh FY. A cautionary note on the analysis of extreme data with Cox regression. *Amer Stat.* 1995;49(2):226-228.

Collet D. Modelling survival data in medical research. London; Chapman & Hall; 1995.

13. Appendices

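### On its plain wording, the Part B sustained-remission denominator can lose known failures who start open-label sirukumab, because their visits need not fall on Week X

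*SAP*

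**What the plan says.** **Who is counted.** SAP 11.4.1 covers subjects in sustained remission at Week 52 of Part A who entered Part B. Because the study was terminated, it includes "only the subset of subjects who attended the Week X visit of Part B or who discontinued study treatment or withdrew from study" before 10 October 2017.

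**Who fails.** Flare, rescue therapy and treatment change are each failures. On treatment change, 11.4.1 says: "If any OL Sirukumab dose is taken prior or on the Week X visit of Part B, subject will fail the criterion".

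**Which visits apply.** Protocol Table 3 ("Subjects NOT Receiving Open-label Sirukumab During Part B") has visits at Weeks 4, 8, 12, 16, 24, 36, 52, 76 and 104 of Part B. A subject who starts open-label drug later than Part B entry moves to Table 5 ("Subjects Receiving Open-label Sirukumab at Any Time AFTER (but NOT immediately Upon) Entry into Part B"), "starting from the visit labelled 'plus 2 weeks' onwards". Protocol section 7 adds: "It is important that upon initiation of open-label sirukumab therapy, the next visit should occur" two weeks after the start. The PLUS 48 visit carries the footnote "Visit only to dispense IP; no assessments are required".

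**How those visits are labelled.** SAP 11.6 adds the offset to the start week. For a start at Week 24, "the visit 2 weeks after initiation of OL Sirukumab will be mapped Week 26 Visit of Part B".

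**What else bears on it.** SAP 11.4.1 refers to 4.6.2.1 for missing data. SAP 8.2.2 carries a failure forward to all later visits for the Part A endpoint; 11.4.1 has no such sentence.

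**The concern.** Whether a subject has a Week X visit depends here on whether the subject has already failed. Responders who stay in remission keep the Table 3 visits and so have a Week X visit. A responder who flares and starts open-label drug follows a schedule counted from that start, which may have no visit at Week X. That subject has not withdrawn and is still being followed, and 11.4.1 already makes the status a failure. If attendance decides inclusion, the subject is nevertheless left out. Only failures can be lost by this route, so any error pushes the reported proportion up.

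The endpoint is how Part B describes maintenance of remission after sirukumab stops. Two programmers reading 11.4.1 could also produce different rates from the same data.

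**Working it through.** **1. The SAP's own mapping.** Mapped week = start week + offset. The two examples in SAP 11.6 reproduce: 24 + 2 = 26 and 12 + 2 = 14.

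**2. Inputs.** Start visits are the scheduled Table 3 visits before Week X, up to Week 52 (Protocol 4.2.2 limits open-label starts to the first 52 weeks of Part B). The Table 5 offsets with assessments are 2, 4, 8, 12, 16, 24, 36, 52 and 76 weeks; PLUS 48 is excluded as dispensing only. A start has an assessed visit at Week X when X minus the start week is one of these offsets.

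**3. Coincidence by Week X.**

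| Week X | Start week (offset needed) | No assessed visit |
|---|---|---|
| 8, 12, 16 | all needed offsets are 4, 8 or 12 | none |
| 24 | 4 (20), 8 (16), 12 (12), 16 (8) | 1 of 4: start 4 |
| 36 | 4 (32), 8 (28), 12 (24), 16 (20), 24 (12) | 3 of 5: starts 4, 8, 16 |
| 52 | 4 (48, dispensing only), 8 (44), 12 (40), 16 (36), 24 (28), 36 (16) | 4 of 6: starts 4, 8, 12, 24 |
| 104 | last visit is fixed at 104 weeks in Part B | none |

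In every missed case the nearest assessed mapped visit is at least 4 weeks from Week X, so the ±5-day visit window does not close the gap. The ±14-day mapping in SAP 8.3.1 would not close it either, and it is written for patient- and physician-reported outcomes only.

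**4. Week 76.** By schedule 5 of 7 starts miss it, but it could not be reached in time. Week 76 of Part B is 52 + 76 = 128 weeks, or 896 days, after Part A baseline. Counted from the original protocol date of 11 May 2015, that is 23 October 2017, after termination on 10 October 2017. Week 104 is later still.

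**5. Illustrative size.** The documents give no Part B rates, so these are assumptions: a share f of responders has started open-label drug by Week X, there are no other failures, and starts are spread evenly over the scheduled visits up to and including Week X. A subject who starts at Week X itself attends that visit and counts as a failure. With m the share of starters who have no Week X visit, the rate shown is (1 − f) / (1 − f·m).

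- Week 24, m = 1/5, f = 30%: 0.70 / (1 − 0.06) = 74.5%.
- Week 36, m = 3/6, f = 30%: 0.70 / (1 − 0.15) = 82.4%.
- Week 52, m = 4/7, f = 30%: 0.70 / (1 − 0.171) = 84.5%.

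All three compare with 70% when every failure is counted. For f = 20% (80% when all are counted) the figures are 83.3%, 88.9% and 90.3%. For f = 40% (60% when all are counted) they are 65.2%, 75.0% and 77.8%.

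**The case against.** The strongest reply is that the exclusion is only one reading.

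- **Missing-data rule.** Under 4.6.2.1 a missing Week X counts as not achieving unless the neighbouring visits are in sustained remission. An open-label starter has already failed, so would be scored a failure and no bias would arise. The same termination sentence stands beside the same kind of reference in the Part A sections, which suggests an administrative cut for subjects who had not reached the visit. This stands as a reasonable reading. However, the text restricts inclusion without saying that 4.6.2.1 is applied first.
- **Undefined term.** Discontinuing study treatment is not defined for Part B. Protocol 4.2.2 has subjects in remission stop blinded drug on entry, so a very literal reading would include everyone and empty the restriction. That is a further ambiguity, and it does not settle the matter.
- **Whether the table exists.** The opening of SAP section 11 limits Part B displays to demographic and baseline characteristics and safety, while 11.1.1 provides a set for Part B efficacy outputs and 11.4.1 specifies this one. It is unclear which governs.
- **Consequence.** SAP 1.1 and section 8 restrict efficacy to summaries. Flares also appear in the Kaplan-Meier summary, the flare counts and the criterion listing. This stands, and it keeps the severity low.

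A reader might infer that the published rate is certainly overstated, that failures usually vanish, or that the Week 24 rate could appear near 90%. The documents do not support these. The first depends on an unstated precedence. The second does not fit Weeks 8, 12, 16 or 104, where no scheduled start is lost, or Week 24, where 3 of 4 starts land exactly on the visit. The third needs every start to fall off schedule, evenly over all whole weeks. Flare visits are possible, but Protocol section 7 and Table 5 footnote 1 describe starting at the scheduled Table 3 visit.

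**Conclusion.** The point holds as a gap in SAP 11.4.1 that can bias the rate in one direction. On the plain wording, known failures who remain in the study can leave the Week X denominator; across Weeks 8 to 52 this affects 8 of 21 combinations of scheduled start and later visit (1 at Week 24, 3 at Week 36, 4 at Week 52). With 30% of responders started on open-label drug and even spread over scheduled visits, the inflation is about 4.5 points at Week 24 and 12.4 points at Week 36. These sizes rest on assumed rates and timing, and on attendance taking precedence over 4.6.2.1. If 4.6.2.1 comes first, the inflation is nil. The actual size cannot be found from the documents. Severity is minor: the output is descriptive, and it is unclear whether it will be displayed.

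**What to change.** In SAP 11.4.1, replace the attendance condition along these lines:

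- The Week X denominator is all Part A Week 52 responders in Part B whose Week X target date, counted from Part B baseline, fell before 10 October 2017, whether or not a visit maps to Week X.
- Anyone with a flare, rescue therapy or any open-label sirukumab dose on or before that target date is not in sustained remission at Week X, nor at any later week that meets the same date limit.
- Section 4.6.2.1 applies before any attendance restriction.

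The date limit is essential. Carrying failures forward without it would count a subject who failed at Week 4 and was terminated at Week 10 at every later week, while a subject still in remission and terminated at Week 10 would be excluded from them. That would bias the rate downward and, at weeks nobody could reach before termination, leave only failures.

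The opening of section 11 should also say whether this table is produced. The cost is a short SAP edit and a small programming change. Reported Part B rates may be somewhat lower.
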